5.7 Number of Subjects

Approximately [REDACTED] subjects will be enrolled in the study. No site may contribute more than [REDACTED] % of the total sample. Assuming 25% attrition from randomization to 6 months in both groups, we expect approximately [REDACTED] evaluable subjects sufficient for the primary endpoint analysis ([REDACTED] %).

5.8 Total Expected Duration of the Clinical Investigation

This protocol assumes the following durations for key steps: approximately [REDACTED] for the payor approval process, approximately [REDACTED] days for the trial period, approximately [REDACTED] months to schedule permanent implant procedure, and [REDACTED] months of follow-up. Based on these assumptions, each subject is expected to be enrolled in the study for approximately [REDACTED] months.

This protocol assumes the following durations for key steps: [REDACTED] months for full enrollment, [REDACTED] months from the time the last subject receives a permanent implant to final follow-up, and [REDACTED] months for study closure. Based on these assumptions, the clinical investigation is expected to take [REDACTED] months.

6.0 TREATMENT AND EVALUATION OF ENDPOINTS

6.1 Enrollment

During Enrollment, the following procedures will be performed:

- Verification of written informed consent
- Inclusion/Exclusion eligibility
- Verification of eligibility by an independent medical monitor

6.2 Baseline

6.2.1 Baseline Clinical Assessments

The baseline visit should occur no later than [REDACTED] days after the enrollment visit. Baseline data will be collected regarding the subject's demographics, health status, and previous treatments for low back pain. The following data will be recorded at baseline:

- Subject demographics including occupational status
- Medical history (pain history and other interventions for pain management)
- Pain condition-related medication use

6.2.2 Baseline Physical Function and Quality of Life Assessments

Baseline data will be collected regarding physical function and quality of life. The following data will be recorded at baseline:

- Numerical Rating Scale (NRS) for low back pain, and leg pain as applicable
- PROMIS-29

This confidential document is the property of Abbott and shall not be reproduced, distributed, disclosed or used without the express written consent of Abbott

Clinical Investigation Plan

- painDetect questionnaire
- Pain Catastrophizing scale (PCS)
- Oswestry Disability Index (ODI)
- Exercise frequency

6.3 Randomization

After enrollment has been completed, subjects will be randomized (3:2 ratio) to either the SCS arm or the CMM arm. Randomization will be stratified by site.

6.4 Conventional Medical Management (CMM arm)

During the follow-up period, subjects in the CMM arm will receive supervised medical care, including medication optimization and supervised non-interventional therapy. Medication optimization should include use of non-steroidal anti-inflammatories and muscle relaxants, as appropriate. Supervised non-interventional therapy may include, but is not limited to, physical therapy, chiropractic care, back school, cognitive behavioral therapy, and acupuncture. Interventional therapy such as injections and radiofrequency ablation, is also allowed. Patient reported outcomes should be assessed after each patient interaction and therapy adjustment(s) (i.e. medication change) made as needed in order to optimize pain control.

6.5 Spinal Cord Stimulation (interventional arm)

A successful trial, defined as 50% decrease in pain recorded on Numerical Rating Scale is required for a subject to receive a permanent implant.

6.5.1 Procedures Involved in the Use of the Device Under Investigation

Descriptions of procedures associated with each device can be found in their respective IFU.

6.5.2 Trial Period

Subjects randomized to receive spinal cord stimulation will first undergo a trial of the therapy. The trial period implementation should start no more than [REDACTED] days after the Baseline visit and should last at least 4 days. Only percutaneous leads may be used for the trial procedure. "On the table" trials and the use of paddle leads for the trial procedure are not allowed.

The following data will be recorded at trial implementation:

- Trial system details
- Device programming
- Device- and/or procedure related adverse events (if applicable)
- All serious adverse events (if applicable)
- Withdrawal (if applicable)

6.5.3 End of Trial Period

The End of Trial Period data collection will occur after the trial period. At this visit, the following data will be recorded:

This confidential document is the property of Abbott and shall not be reproduced, distributed, disclosed or used without the express written consent of Abbott

Clinical Investigation Plan

- NRS for back pain, and leg pain as applicable
- Patient reported pain relief
- Device- and/or procedure related adverse events (if applicable)
- All serious adverse events (if applicable)
- Withdrawal (if applicable)

6.5.4 Permanent System (if applicable)

Subjects reporting at least 50% improvement in back pain NRS and wish to proceed with the study will receive a permanent implant. The procedure will be performed according to the IFU. Permanent implant should be performed no later than 45 days after the end of the trial period.

6.5.5 Procedures Involved in the Use of the Device Under Investigation

Descriptions of procedures associated with each device can be found in their respective IFU.

6.5.6 Permanent System Implementation

The spinal cord stimulator will be activated and programmed by trained personnel either during post-operative recovery or at an office visit in accordance with standard operating procedures. The subject's spinal cord stimulator will be programmed according to the most recent Abbott programming guidance. After programming, the subject will receive a patient programmer and will be instructed on how to use the system to relieve their pain. Subjects will be able to adjust the stimulation to ensure the best results.

The following data will be recorded during permanent implementation:

- Spinal cord stimulator system details
- Surgical procedure details
- Device programming (if applicable)
- Device- and/or procedure related adverse events (if applicable)
- All serious adverse events (if applicable)
- Withdrawal (if applicable)

6.6 Follow-up Assessments

6.6.1 Follow-up for All Subjects (Site/Office/Telemedicine Visit or Telephone Call)

Required follow-up visits will occur at [REDACTED] month (\pm 14 days), and at [REDACTED] (\pm 30 days), and [REDACTED] -months (\pm [REDACTED] days) after randomization or permanent implantation.

Patient reported outcomes should be assessed after each follow-up visit and therapy adjustment(s) (i.e. reprogramming) made as needed in order to optimize pain control. Ongoing technical reprogramming assistance will be provided by the sponsor.

The following data will be collected at each visit:

- Occupational status
- Pain condition-related medication use
- Patient-reported pain relief (PRPR)
- NRS for back pain, and leg pain as applicable
- PROMIS-29

This confidential document is the property of Abbott and shall not be reproduced, distributed, disclosed or used without the express written consent of Abbott

Clinical Investigation Plan

- Pain Catastrophizing scale (PCS)
- Oswestry Disability Index (ODI)
- Patient Global Impression of Change (PGIC)
- Exercise frequency
- Patient satisfaction with therapy
- Device- and/or procedure related adverse events (if applicable)
- System revision (if applicable)
- Protocol deviation (if applicable)
- Device programming (if applicable)
- All serious adverse events (if applicable)
- Withdrawal (if applicable)

If a study participant is unable or unwilling to attend an in-person visit, the visit may be conducted remotely using telemedicine as provided by the study center. Questionnaires may be administered during the remote visit. The Coordinator or designee must document the subject's responses on the worksheet, note that the responses were collected via phone, save that document as source data, and enter the information in the EDC system. Alternately, questionnaires may be mailed to the participant in a return postage provided envelope. If this method is chosen, the Coordinator or designee should schedule a call with the subject to clearly explain the questionnaires and answer any questions the subject may have.

6.6.2 Patient Reported Outcome (PRO) Measures

The Investigator, Coordinator or site designee will administer the patient-reported outcome questionnaires via paper for later transcription to EDC, or electronically. If the subject reported outcome questionnaire is provided to the subject electronically, the source data will be available in the EDC system for the site's records. It is important the subject understands the meaning of all words and instructions in the questionnaires. The subject should be instructed to ask any questions about the questionnaires, if further explanation is needed. Once the questionnaires are completed, the Coordinator or designee will review for completeness to verify that all questions have been answered according to the directions provided. If the subject is unable to attend a follow up visit in person, questionnaires may be sent to the subject and returned to the site. The Coordinator or designee should schedule a call with the subject to clearly explain the questionnaires and answer any questions the subject may have.

Alternatively, If the subject is unable to attend a follow up visit in person, the Investigator or designee may also schedule a phone call or telemedicine visit with the subject to review the questionnaires. The Coordinator or designee should document the subject's responses on the worksheet, note that the responses were collected via phone, save that document as source data, and enter the information in the EDC system.

- Patient Global Impression of Change (PGIC)
- Patient-reported pain relief (PRPR)
- Numerical Rating Scale (NRS)
- PainDetect (PD-Q)
- Oswestry Disability Index (ODI)
- PROMIS-29
- Pain Catastrophizing Scale (PCS)

Clinical Investigation Plan

6.6.2.1 Patient Global Impression of Change (PGIC)

The PGIC is a categorical rating scale used to evaluate the subject's impression of change in his/her condition since the beginning of the study treatment. The subject will be requested to rate their overall change in activity limitations, symptoms, emotions and overall quality of life related to his/her condition on a seven-point categorical scale via an interview technique. The categories are as follows: 1- no change, 2- almost the same, 3 - a little better, 4 - somewhat better, 5-moderately better, 6 - better, and 7- a great deal better. Although this tool does not specify the area of change (e.g., pain, function, quality of life, etc.), it allows for an overall integrated assessment from the prospective of the subject. PGIC values of 6 or 7 are reported to correlate best with actual change (23, 24).

6.6.2.2 Patient-reported pain relief (PRPR)

The PRPR asks a subject to state the percentage pain relief they receive from their treatment. The scale ranges from 0% = no relief to 100% = complete pain relief.

6.6.2.3 Numerical Rating Scale (NRS)

The pain NRS consists of 1 question that will be asked by interviewing the subjects. Patients will be asked to rate, from 0 (no pain) to 10 (worst imaginable pain), their average pain over the past 24 hours specific to the area(s) of chronic pain being treated. A higher score indicates greater pain intensity

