3.2 Measures Taken to Avoid and Minimize Bias

An independent Clinical Events Committee (CEC) will adjudicate all serious and non-serious device and procedure related adverse events, and all death events.

An independent board-certified spine surgeon will act as a medical monitor and evaluate each enrolled subject for suitability.

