4.0 ENDPOINTS

4.1 Primary Effectiveness Endpoint and Rationale

The primary effectiveness endpoint is the difference in responders between groups at 6 months. A subject is considered a responder for the primary endpoint if the following criterion is met:

- Improvement in pain, defined as a $\geq 50\%$ decrease on NRS

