11.3 Source Documentation

Regulations and GCP require the Investigator to maintain information in the subject's original medical records that corroborates data collected on the CRFs. To comply with these regulatory requirements/GCP, sites should include the following information in the subject record at a minimum and if applicable to the clinical investigation:

- Medical history/physical condition of the subject before involvement in the clinical investigation sufficient to verify CIP entry criteria
- Dated and signed notes on the day of entry into the clinical investigation referencing the Sponsor, CIP number, subject ID number, and a statement that informed consent was obtained
- Dated and signed notes from each subject visit (for specific results of procedures and exams)
- Notes regarding CIP-required and prescription medications taken during the clinical investigation (including start and stop dates)
- Subject's condition upon completion of or withdrawal from the clinical investigation
- Any other data required to substantiate data entered into the CRF
- Patient reported outcome measures may be completed using CRF worksheets. This serves as source documentation.
- Patient reported outcome measures may be completed by the patient electronically on PRO-Q application. The electronic CRF output will serve as source documentation.
- Adverse events reported and their resolution, including supporting documents, such as discharge summaries, consult reports, office notes, x-ray results, lab results and other source documents as applicable per the reported AE. The documentation of site awareness of SAEs and of investigator assessment of device relationship for SAEs should be included.

Clinical Investigation Plan

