1.6 Blinding

For this study, the subject, site personnel, and some sponsor personnel will be aware of treatment assignment. Sponsor statisticians, including the DISTINCT Study Statistician, will not have access to any data that combines outcomes with treatment assignment prior to performing the primary endpoint analysis of the randomized cohort.

Statistical Analysis Plan

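### The NRS that alone defines the primary endpoint is specified as an interview by site staff who know the assignment, while other sections permit self-completion; no single mode is fixed for baseline and month 6

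*Protocol*

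**What the plan says.** Protocol 4.1 states: "The primary effectiveness endpoint is the difference in responders between groups at 6 months". A responder is a subject whose NRS falls by at least 50%, and nothing else enters the definition. Protocol 8.9 and SAP 2.7 make study success depend on this comparison.

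The documents describe how the NRS is obtained in three places:

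- Protocol 6.6.2.3, on the instrument itself: "The pain NRS consists of 1 question that will be asked by interviewing the subjects". It does not name the interviewer.
- Protocol 6.6.2, on all patient-reported outcomes, with the NRS in the list that follows: "The Investigator, Coordinator or site designee will administer the patient-reported outcome questionnaires via paper for later transcription to EDC, or electronically". For subjects who cannot attend, forms may be sent out. Alternatively, staff may take the answers remotely and must "note that the responses were collected via phone, save that document as source data, and enter the information in the EDC system".
- Protocol 11.3, on source documents: worksheets may be used, and "Patient reported outcome measures may be completed by the patient electronically on PRO-Q application".

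On blinding, SAP 1.6 says that "the subject, site personnel, and some sponsor personnel will be aware of treatment assignment". Protocol 3.2, on limiting bias, has two measures. One is adjudication of adverse events and deaths by an independent committee. The other reads: "An independent board-certified spine surgeon will act as a medical monitor and evaluate each enrolled subject for suitability". Neither concerns collection of the NRS.

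**The concern.** A pain score given aloud to someone who knows the treatment, and may have helped deliver it, can be shaped by how the question is put and by the wish to give a welcome answer. In an open-label trial that influence need not be equal in the two arms. Here it would act on the one item that decides the trial.

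The subject cannot be blinded in this design, but the interviewer's part in the score can be taken out, and the study already has the means. Because the endpoint is a within-subject percentage change, it also matters that the same mode is used at baseline and month 6. The sections as written do not secure that.

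**Working it through.** **1. The sections side by side.**

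| Question | Where | Answer |
|---|---|---|
| How is the NRS obtained? | Protocol 6.6.2.3 | By interview |
| Who administers patient-reported outcomes? | Protocol 6.6.2 | Investigator, coordinator or site designee |
| Do they know the assignment? | SAP 1.6 | Yes, site personnel do |
| Is a blinded or independent interviewer described? | Protocol 3.2, 6.6.2; SAP 1.6 | No |
| Is self-completion possible? | Protocol 6.6.2, 11.3 | Yes, on paper or PRO-Q |
| Is one mode required for baseline and month 6? | Protocol 6.2.2, 6.6.1, 6.6.2 | No |
| Must the NRS precede therapy adjustment at the visit? | Protocol 6.4, 6.6.1 | Not stated |
| Does any primary sensitivity analysis use mode? | SAP 2.3.1.2, 2.12 | No: multiple imputation, mITT and PTE only |

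That the interviewer is site staff follows from reading 6.6.2.3 with 6.6.2. Within 6.6.2, only the NRS and the PGIC are described as interviews. The ODI is self-completed, and the PROMIS-29 is read and ticked by the subject. The verbal rating at the phone-call visits does not matter here, because SAP 1.3 places those visits at 15 and 21 months.

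**2. The plan's own figure.** Inputs from SAP 2.4: about 200 randomized in Phase I, 3:2 allocation, 25% attrition, 45% v 20%, two-sided alpha 0.05. The test, from SAP 2.3.1.1, is the Z-test with unpooled variance.

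- Evaluable: 200 × 0.75 = 150, split 90 SCS and 60 CMM.
- SE = √(0.45 × 0.55/90 + 0.20 × 0.80/60) = 0.0736.
- Power = Φ(0.25/0.0736 − 1.96) = Φ(1.437) = 92.5%.
- Exact binomial enumeration of the same test gives 91.5%.

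The stated power of at least 90% reproduces. Nothing in this point disputes it.

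**3. Illustration of what a shift would do.** The documents give no interviewer effect, so the shifts below are assumptions. Take true response of 20% in both arms and add b points to observed SCS response only. The last column sums the exact binomial probabilities of every outcome at 90/60 where (p̂_SCS − p̂_CMM)/SE exceeds 1.96.

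| Assumed shift b | SCS subjects reclassified (90 × b) | Observed rates | Chance of a false SCS win |
|---|---|---|---|
| 0 | 0 | 20% v 20% | 2.9% |
| 3 points | 2.7 | 23% v 20% | 7.1% |
| 5 points | 4.5 | 25% v 20% | 11.7% |
| 10 points | 9 | 30% v 20% | 30.5% |

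The 2.9% in the first row is the test's own exact upper-tail error at these sizes, against a nominal 2.5%. A shift of the same size from any other cause would give the same figures. The table shows how sensitive the result is; it is not evidence that such a shift occurs.

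**The case against.** The strongest reply is that self-completion is already allowed. Protocol 6.6.2 lists the NRS among measures given on paper or electronically, and 11.3 lets the patient use PRO-Q. That stands. A reader might infer that every primary NRS will be taken by an unblinded interviewer, and the documents do not support that. They permit self-completion in one place and specify interview in another. For the same reason, interviewer influence and mixed modes cannot both be claimed at full strength: if 6.6.2.3 governs, the mode is largely uniform; if 6.6.2 governs, an interview is not required.

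Two further inferences are tempting and fail. One is that mode will differ by arm: no section ties mode to arm, and the remote options apply to everyone. The other is that sponsor staff collect the score: Protocol 6.6.1 gives the sponsor technical help with reprogramming, while 6.6.2 gives questionnaire administration to the site.

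It is also fair to say that subjects know their treatment, so self-entry leaves their expectation, and some social desirability, in place. The self-completed ODI and the PROMIS-29 pain item offer a cross-check, although neither is planned as a sensitivity analysis for the primary endpoint. Phone collection must already be noted in the source. The case report forms are under separate cover and the Schedule of Events is redacted, so either may name a mode.

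A strict rule has a cost as well. Apart from trial failures, SAP 2.3.1.1 requires month-6 data for inclusion in the primary analysis, so refusing interviewed scores could lose subjects. Barring all staff contact before entry would conflict with the explanation and completeness check in 6.6.2. Both points limit the remedy. They do not justify leaving the mode open.

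**Conclusion.** The concern holds in a limited form. For the sole primary measure, Protocol 6.6.2.3 conflicts with 6.6.2 and 11.3. Under the interview rule, the score passes through site staff who know the assignment. No bias measure or sensitivity analysis in the documents addresses this, and a self-completed alternative already exists. This is an avoidable source of bias and should be corrected, but it is not proof that the result will be biased.

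Its size is unknown. The 7.1% and 11.7% rest on assumed shifts of 3 and 5 points, wholly in favour of SCS, with true response of 20% in both arms and 90 and 60 evaluable subjects. No sample-size or power figure in the plan changes. A reader might infer that self-completion would free the endpoint of open-label bias; it would remove the interviewer's influence only.

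**What to change.** Reconcile Protocol 6.6.2, 6.6.2.3 and 11.3 to say that:

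- at baseline and month 6, in both arms, the subject enters the NRS personally on PRO-Q, with paper as back-up;
- at each of these visits the entry is made before any therapy adjustment or reprogramming;
- staff only explain the form and check that it is complete;
- interview or phone remains a fallback, with the mode recorded on the case report form at each time point.

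In SAP 2.3.1.2, state that fallback values stay in the primary analysis and add a sensitivity analysis by mode. It should also cover subjects whose baseline was already taken by interview, so that the change does not create an unexamined mismatch between baseline and month 6. Simply dropping fallback values would remove remote subjects selectively, so that should not be the only analysis by mode.

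The cost is protocol and SAP wording, brief site training, one mode field, and a link or mailed form for remote visits. Sample size and treatment are unaffected.

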6.6.2.4 PainDETECT Questionnaire (PD-Q)

The painDETECT (PD-Q) is a validated self-reported questionnaire that discriminates between neuropathic and nociceptive pain components in patients with chronic pain. The PD-Q is comprised of three sections: gradation of pain (7 questions), pain course pattern (1 question), and radiating pain (1 question). Each question addresses the quality of neuropathic pain symptoms and is scored individually. Gradation of pain questions are scored from 0-5. The pain course pattern question score ranges from -1 to +1, and the radiating pain question score ranges from +2/0. The overall PD-Q score ranges from 38 to -1. The higher the score, the higher the likelihood of a neuropathic pain component. A score ≤ 12 suggests that a neuropathic pain component is unlikely. Scores ≥ 19 suggest that a neuropathic pain component is likely. Scores between 12 and 19 suggest that the presence of a neuropathic pain component is unclear and requires further examination to ensure a proper diagnosis. The sensitivity of this tool was validated by Freyhagen et al. at 84% (25).

